A total of approximately 70 participants will be recruited for this study. Both males and females from diverse racial and ethnic backgrounds will be recruited using IRB approved procedures. Potential participants will be recruited from our contacts in the community including other MGH

clinicians, as well as through local and national support groups and list serves using IRB approved recruitment materials. MGH child psychologists may also refer potentially eligible participants. In each case, interested participants will be directed to our pre-screen REDCap survey and will be given the option to contact the study staff to learn more about the study.

IV. SUBJECT ENROLLMENT

Methods of enrollment

Participants will contact the PI or study staff by telephone, email, or by completing our IRB approved pre-screen REDCap survey in response to advertisements. Subject will be contacted by phone, informed about the study and given a pre-screen REDCap to determine whether they meet inclusion/exclusion criteria (see the attached pre-screening questionnaire). Subjects may also be referred to the study. Subjects must respond “yes” to all inclusion criteria and “no” to all exclusion criteria to be eligible for the study. Eligible participants will be consented and will complete the baseline survey online into REDCap, a secure, web-based application designed to support data capture for research studies.

Randomization

After enrollment, participants will be randomized to the Immediate intervention group (IG) or Waitlist control group (WG). Randomization will be conducted using a random plan generator, with 1:1 randomization. The WG will begin their program approximately 3 months after the SMART-3RP group. For both groups, the intervention will last approximately 8 weeks, weekly with groups meeting once per week for approximately 1 hour.

Informed consent process

Eligible and interested participants will be sent a consent form and scheduled for a phone consent. Informed consent and authorization will be obtained and documented through use of a written consent form approved by the Partners Human Research Committee (PHRC) and signed by the participant. The PI or qualified study staff will complete informed consent procedures.

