Acceptability will be assessed using a Participant Feedback questionnaire (See Feedback questionnaire attached).

2) Is the virtual SMART-3RP program effective for parents of children with learning disabilities?

a) Is there a significant difference in primary and secondary outcome measures between participants in the Immediate and Waitlist SMART-3RP groups at 3 mo. post enrollment?

We will use paired samples t-tests to compare within group differences on primary and secondary outcome measures from 3 mo. to baseline for the Immediate and Waitlist Groups. Primary outcome measures are the General Self-Efficacy Questionnaire (GSE), Current Experiences Scale (CES; from the Post Traumatic Growth Inventory), and the Visual Analogue 0-10 scales (VAS; measuring stress, distress, coping, and physical discomfort). Secondary outcome measures are: the Measure of Current Status-A (MOCS-A; to assess stress reactivity), Cognitive and Affective Mindfulness Scale-Revised (CAMS-R; to assess growth enhancement), and the Parental Stress Scale (PSS; to assess parental stress).

We will then use independent samples t-tests to compare the difference between the Immediate group's 3 months post enrollment and baseline assessment results with the

difference between the waitlist group's 3 months and baseline assessment results on primary and secondary outcome measures.

b) Among participants randomized to both conditions, will there be improvements in primary and secondary outcome measures from pre-post SMART-3RP (IG: assessments from baseline-3 mo.; WG: from 3-6 mo.)?

We will use paired samples t-tests to compare all primary and secondary assessments from pre-post SMART-3RP (for the IG, assessments are from baseline-3 mo.; for the WG, assessments are 3 mo. to 6 mo.).

c) Among the Immediate group only, will the changes from baseline to 3 months post enrollment (end of treatment) be sustained at 6 months post enrollment (3 months post treatment)?

We will use paired samples t-test to assess within-group differences in long-term outcomes. We will compare measures at the 6 months assessment to measures at the 3 months assessment for the Immediate group.

3) Will the virtual delivery SMART-3RP be effective in reducing participants' stress levels, measured by hair cortisol?

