STATISTICAL ANALYSIS PLAN

March 26, 2019

NCT# 02772432

Development of a Resiliency Training Program for Parents of Children With Specific

Learning Disabilities

Randomization

We asked participants for their daytime or evening time preferences prior to randomizing them to the intervention or control from November 2016 to September 2017, balancing for group size. Participants were randomized using a random plan generator, with 1:1 randomization.

Statistical Analyses

To assess study feasibility, we assessed enrollment, intervention session attendance (>6) and retention at time 2 (75% response; intervention group: end of treatment; wait-list control: 3-month post-enrollment) and time 3 (intervention group: 3-months post end-of treatment; wait-list control: end of treatment). Study completers and non-completers at time 2 were compared on baseline demographic characteristics using independent samples t-tests for continuous variables and Chi-square tests or Fisher's exact tests for categorical variables. To assess study acceptability, we reviewed participant self-report survey feedback (e.g., satisfaction with the number and length of intervention sessions, comfort level with group sessions, continued RR practice) and open-ended qualitative program feedback. To explore preliminary efficacy of the intervention to improve our proposed psychosocial outcomes, we first characterized the two randomized groups (intervention group and wait-list control) by baseline demographic factors and reviewed baseline psychosocial data for univariate distributions. We then used all available data to test between-group (intervention group versus wait-list control) differences in change scores from time 1 to time 2 (intervention group: end of treatment; wait-list control: 3-month post-enrollment) using independent samples t-tests. Using the intent-to-treat principle, we replicated the analysis using multiple imputation⁶⁶ (five imputed datasets) to address missingness at time 2.

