We followed our main preliminary efficacy analyses with a series of paired samples t-tests using all available data, to further characterize results. First, we evaluated changes in scores from time 1 to time 2 within each randomized group. To further explore intervention efficacy, we evaluated the combined change from pre- to post-intervention across intervention group condition participants (using time 1 to time 2 data) and wait-list control participants (using time 2 to time 3 data). Finally, we explored potential maintenance of intervention benefits by evaluating change in scores from time 2 to time 3 within the intervention group only. Additionally, to support a future larger scale trial, including identification of a potential moderator of intervention effects, we explored whether greater parenting stress at baseline was associated with greater changes in our proposed psychosocial outcomes among participants (before treatment and end of treatment) using Pearson correlations.

Running head: A VIRTUAL INTERVENTION PROMOTING RESILIENCY FOR PARENTS OF CHILDREN WITH LAD Analyses were conducted using IBM SPSS version 23.

Running head: A VIRTUAL INTERVENTION PROMOTING RESILIENCY FOR PARENTS OF CHILDREN WITH LAD

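### The pooled pre-post paired t-test has no comparator but is labelled as exploring efficacy; efficacy conclusions should rest only on the randomised time 1 to time 2 comparison

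*SAP*

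**What the plan says.** The SAP (Statistical Analyses) uses independent-samples t-tests "to test between-group (intervention group versus wait-list control) differences in change scores from time 1 to time 2" and repeats them under multiple imputation. This is the controlled analysis, and the SAP treats it as the main one.

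Paired tests come next: "We followed our main preliminary efficacy analyses with a series of paired samples t-tests using all available data, to further characterize results". They are:

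- time 1 to time 2 change within each arm;
- a pooled change made of the intervention arm's time 1 to time 2 data and the wait-list arm's time 2 to time 3 data, introduced with "To further explore intervention efficacy, we evaluated the combined change from pre- to post-intervention";
- time 2 to time 3 change in the intervention arm, for maintenance.

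The protocol (section VI, question 2) groups its tests under this question: "Is the virtual SMART-3RP program effective for parents of children with learning disabilities". Item 2(a) begins with "We will use paired samples t-tests to compare within group differences on primary and secondary outcome measures" and only then turns to the between-arm test. Item 2(b) applies paired tests to the same two treated periods. Section II gives that pre-post change its own secondary aim, with a hypothesis of improvement.

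Neither document says that a time trend or regression to the mean could explain a pre-post change.

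**The concern.** Every change score in the pooled test comes from a period in which the parent received the programme. There is no untreated period and no term for calendar time or visit. A non-zero mean change is therefore the sum of any programme effect and whatever improvement would have happened anyway, and the test cannot separate them.

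The pooled test is also the more sensitive of the two: it uses both arms and estimates a single mean rather than a difference of means. It can easily be significant when the randomised comparison is not. With the efficacy label attached, that pattern invites the reading that the programme works. The SAP also says that its exploratory work is meant to support a larger trial, and a pre-post change inflated by drift would mislead the planning of that trial.

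**Working it through.** The documents give no alpha, power, effect size or SD, and no derivation of the sample size, so there is no figure to reproduce. The check asks how often each test is significant when the programme does nothing.

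**Inputs**

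- Total size: "A total of approximately 70 participants will be recruited for this study" (protocol, section III).
- Allocation 1:1 (SAP, Randomization), so 35 per arm.
- Retention benchmark at time 2: 75% (SAP). 0.75 × 70 = 52.5, taken as 52, or 26 per arm. This is a time 2 figure. The wait-list half of the pooled test needs time 3 data, for which the SAP gives no percentage.
- Assumed: two-sided 5% level; programme effect zero; untreated improvement (drift) of d SDs of the change score, the same in both arms.

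**Pooled paired test, equal drift in both periods**

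With n parents the t statistic is noncentral t with n − 1 degrees of freedom and noncentrality d√n. The rejection probability is P(|t| > t₀.₉₇₅,ₙ₋₁).

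| Drift d | d√52 | Significant, n = 52 | d√70 | Significant, n = 70 |
|---|---|---|---|---|
| 0 | 0 | 5% | 0 | 5% |
| 0.1 | 0.72 | 11% | 0.84 | 13% |
| 0.2 | 1.44 | 29% | 1.67 | 38% |
| 0.3 | 2.16 | 57% | 2.51 | 70% |

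A simulation with 40,000 runs (three visits, unit SD, correlation 0.5, so that the change score also has SD 1) agrees with the formula at 0.2 and 0.3 SD.

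**Drift in the first period only**

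If parents enrol at a bad time and have recovered by time 2, only the intervention half of the pooled test carries the drift. The pooled mean is then biased by d/2. For d = 0.3 the bias is 0.15 SD, and the simulated rejection rates are about 18% (n = 52) and 23% (n = 70).

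**Randomised between-arm test**

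Drift common to both arms over time 1 to time 2 cancels in the difference. The simulated rejection rate was about 5% in every scenario.

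**Why the two tests can disagree**

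In SDs of the change score, the standard error of the pooled mean at n = 70 is 1/√70 = 0.12. That of the between-arm difference is √(2/35) = 0.24, twice as large. At 80% power the pooled test detects 0.34 SD (n = 70) or 0.40 SD (n = 52). The between-arm test detects 0.68 SD (35 per arm) or 0.79 SD (26 per arm). With no programme effect and 0.3 SD drift in both periods, the pooled test was significant while the randomised test was not in 54% of simulated trials (26 per arm) and 67% (35 per arm).

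**How large could drift be?**

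The documents do not say. As an illustration, if parents enrol 0.5 SD worse than their usual level and the retest correlation is r, the expected untreated improvement is (1 − r) × 0.5 score SD: 0.25 at r = 0.5 and 0.15 at r = 0.7.

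**The case against.** The strongest reply is that the plan already has the right hierarchy. The between-arm comparison is the main efficacy analysis, and it subtracts exactly the wait-list arm's untreated change. The paired tests come afterwards, in exploratory language, within a self-described pilot. The SAP also tests the wait-list arm's untreated time 1 to time 2 change by itself, so a large drift would be visible beside the pooled result. No decision rule turns a significant paired test into a claim of success.

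All of this stands, and it limits the point to supporting evidence. A reader might infer that the trial's efficacy conclusion as a whole rests on uncontrolled tests. The documents do not support that.

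A reader might also take 57% or 70% as the expected false-positive rate. That is not supported either. Those figures need 0.3 SD of drift in both periods. Entry has no stress or resiliency threshold, so regression to the mean is possible but not shown. The wait-list arm's pre-programme score is taken about three months after enrolment, when much of any such regression may be over. Front-loaded drift gives the lower figures of about 18% and 23%.

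What survives is the label. Exploratory status can excuse low power or multiple testing. It does not make an uncontrolled change attributable to the programme, and showing the wait-list drift in a separate test does not remove it from the pooled one.

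**Conclusion.** The point holds as one about supportive analyses and their interpretation; the main analysis is sound. The pooled test, and the within-arm tests of change during the programme, cannot distinguish a programme effect from spontaneous improvement, yet both documents attach efficacy or effectiveness wording to them.

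The size depends on drift that the documents do not quantify. Over the range examined, the pooled test's false-positive rate runs from the nominal 5% with no drift to 57% (n = 52) or 70% (n = 70) at 0.3 SD in both periods. The randomised test is unaffected by drift common to both arms. The 5% level, the drift sizes and the use of time 2 retention for a test that also needs time 3 data are assumptions. The change is worth making because it removes a biased route to an efficacy claim at almost no cost.

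**What to change.** In the SAP, and in section VI, question 2 of the protocol, state that conclusions on efficacy rest only on the between-arm comparison of time 1 to time 2 change. Report the pooled and within-arm changes as descriptive means with confidence intervals. Remove the significance tests and the efficacy wording from them, and note that these changes include any time trend.

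I would not substitute a comparison of each wait-list parent's treated change with the same parent's earlier untreated change. It assumes a steady trend, so improvement concentrated soon after enrolment would bias it against the programme. It is also imprecise. Under equal correlation between visits its variance is 6(1 − r)s², against 2(1 − r)s² for a single change, so its standard error is √3 = 1.73 times as large. At 80% power it detects about 0.99 SD of change with 26 parents or 0.84 SD with 35, worse than the randomised test.

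The cost is a change of wording and of table format, with no new data. The real downside is that the more sensitive pooled test can no longer support an efficacy claim, which leaves the between-arm test with its detectable difference of 0.68 to 0.79 SD.

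### Imputation and the completer comparison stop at time 2, so the maintenance test and the Waitlist half of the pooled pre-post test rest only on parents with both time 2 and time 3 scores

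*SAP*

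**What the plan says.** The SAP (Statistical Analyses) tests the between-arm difference in change from time 1 to time 2 with independent-samples t-tests. It then repeats that test under the intent-to-treat principle: "we replicated the analysis using multiple imputation⁶⁶ (five imputed datasets) to address missingness at time 2". Its one check on who was lost is also tied to time 2: "Study completers and non-completers at time 2 were compared on baseline demographic characteristics".

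The analyses that follow are paired t-tests on whatever data are available. Two of them need time 3:

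- The pooled pre-post test takes time 1 to time 2 from the Immediate arm (the SAP's intervention group) and time 2 to time 3 from the Waitlist arm.
- The maintenance test is described as "evaluating change in scores from time 2 to time 3 within the intervention group only".

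Retention at time 3 is listed as a feasibility measure, "time 3 (intervention group: 3-months post end-of treatment; wait-list control: end of treatment", but no response figure, missing-data method or completer comparison goes with it. The protocol (VI. Biostatistic Analysis, questions 2b and 2c) plans the same paired tests and names no method for missing data. Both tests answer secondary aims in the protocol (II. Specific Aims).

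**The concern.** A paired t-test uses only people who have both scores. An Immediate parent who answers at end of treatment and not at time 3 leaves the maintenance test, and so does one who answers at time 3 but missed time 2. The same rule decides which Waitlist parents enter the pooled test, where time 3 is their end-of-treatment score. Loss there affects an estimate of improvement, not only one of durability.

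The SAP treats missing scores as a threat at time 2 and gives no reason for leaving time 3 out. Data that could help are collected: baseline scores, time 2 scores from those who answered, and sessions attended. If loss is related to these, the available-case estimates can be biased and the reader has no means to judge it.

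Precision matters as well. Neither document sets a margin or rule for calling a gain sustained. A non-significant change in a reduced sample could be taken as maintenance, although the SAP does not say it will be read that way.

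**Working it through.** The documents give no power, effect size or standard deviation for these tests, so there is no planned figure to reproduce. The check has three parts.

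**1. Number of pairs**

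Inputs:
- Sample size: "A total of approximately 70 participants will be recruited for this study" (Protocol, III. Subject Selection, Recruitment).
- Allocation: "Participants were randomized using a random plan generator, with 1:1 randomization" (SAP, Randomization). This gives 70 / 2 = 35 per arm.
- Time 2 response: "retention at time 2 (75% response; intervention group: end of treatment; wait-list control: 3-month post-enrollment" (SAP, Statistical Analyses). The text does not say whether 75% is a target or a result.
- Time 3 response: not given. Assumed 75% of those randomized.

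Results per arm:
- Responders at each survey: 0.75 × 35 = 26.25, about 26.
- Most pairs (the same parents answer both): 26, or 26/35 = 74% of the arm.
- Fewest pairs (least overlap): 26 + 26 − 35 = 17, or 17/35 = 49%.
- Independent losses: 35 × 0.75 × 0.75 = 19.7, about 20.

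For the pooled test, assume every parent has a baseline score. The Immediate half then has about 26 pairs and the Waitlist half 17 to 26, so 43 to 52 of 70 parents contribute (61% to 74%).

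**2. Precision**

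The standard error of a mean change goes with 1/√n. Compared with 35 pairs it rises by √(35/26) = 1.16, √(35/20) = 1.32 or √(35/17) = 1.43 times.

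Assume a two-sided 5% level and a true decline of 0.3 standard deviations of the change. Power of the paired t-test is then 41% with 35 pairs, 31% with 26 and 26% with 21 (21 corresponds to an assumed 60% of the arm). These figures assume that dropout is unrelated to outcome.

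**3. Direction of bias**

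Assume a true mean change from time 2 to time 3 of −0.30, with 75% staying. Let staying depend on a normal latent variable. The standardized mean of that variable among those who stay is φ(0.674)/0.75 = 0.318/0.75 = 0.424.

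- If staying has correlation ρ with the change itself, the mean change among stayers is −0.30 + 0.424ρ, in standard deviations of the change.
- If staying has correlation ρ with the time 2 score, and scores at times 2 and 3 correlate 0.6 (assumed), the mean change among stayers is −0.30 + (0.6 − 1) × 0.424ρ, in standard deviations of the score.

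| Who stays | Assumed ρ | Mean change among stayers (truth −0.30) |
|---|---|---|
| Unrelated to outcome | 0 | −0.30 |
| Parents who hold their gains | +0.3 to +0.5 | −0.17 to −0.09 |
| Parents who lose their gains | −0.3 to −0.5 | −0.43 to −0.51 |
| Parents with good time 2 scores | +0.5 | −0.38 |
| Parents with poor time 2 scores | −0.5 | −0.21 |

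A simulation of the same set-ups gave these values to two decimals. The sign of the bias depends on the dropout pattern, and the documents do not describe one. The last two rows are the kind of bias that a method using earlier scores can correct. Rows two and three are corrected only as far as earlier data predict the change.

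**The case against.** These are secondary analyses in a pilot, which the SAP presents as exploratory follow-on work. The main between-arm comparison has its imputed repeat and is untouched. The protocol (V. Study Procedures) also acts against non-response: parents who have not answered within two weeks are telephoned, and the 3-month and 6-month surveys each carry a $20 gift certificate. Retention at time 3 is itself reported. All of this stands and keeps the point modest. It does not supply a way to handle the scores that are still missing.

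A missing-at-random method would not recover relapse that earlier data fail to predict. That stands too, and limits what the fix can promise. A joint imputation of every outcome would be unstable: nine scores (GSE, CES, four VAS, MOCS-A, CAMS-R, PSS) at three times is 27 variables on about 35 parents in an arm. The models should therefore be fitted one outcome at a time.

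Time 3 is not the only gap. The within-arm time 1 to time 2 tests and the Immediate half of the pooled test also have no stated imputation. The Pearson correlations with baseline parenting stress would use time 3 if Waitlist parents are included.

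A reader might infer three stronger things, and the documents support none of them:

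- **That the gap favours a finding of maintained benefit.** This needs parents who lose their gains to be likelier to stop answering. Neither document says why parents are lost, and the table above shows that other patterns give no bias or the opposite bias.
- **That time 3 is more prone to loss than time 2.** No time 3 figure is given.
- **That a set share of the gain is hidden.** If every time 2 responder lost by time 3 had returned to baseline and all others held steady, the hidden loss would be 6/26 = 23% with 20 pairs, but 0/26 = 0% with 26 and 9/26 = 35% with 17. That is one constructed scenario, not an estimate.

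**Conclusion.** The point holds in a direction-neutral form. Imputation and the completer comparison end at time 2. The Immediate-arm maintenance test and the Waitlist half of the pooled pre-post test therefore use only parents with both time 2 and time 3 scores. If loss at time 3 is related to earlier scores or attendance, both estimates may be biased, and the direction cannot be known from the documents. Precision falls in any case.

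The expected size is 17 to 26 pairs out of about 35 per arm. This rests on equal arms, 75% response at time 2 (target or result unclear) and an assumed 75% at time 3. The change is worth making because it is cheap and the tests answer stated secondary aims.

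**What to change.** For each outcome separately, do one of the following:

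- Fit a linear mixed model to times 1, 2 and 3 with arm-by-time terms. The maintenance change and the pooled pre-post change are then contrasts of the fitted means. The same model covers the within-arm time 1 to time 2 changes.
- Extend the imputation to time 3 with a small per-outcome model that includes earlier scores and sessions attended.

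Report the maintenance and pooled pre-post changes from that analysis with confidence intervals and numbers of pairs, beside the available-case results. Repeat the completer comparison at time 3, and add baseline scores, time 2 scores and attendance to the demographics.

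The cost is a SAP paragraph and some extra runs, with no new data. The downside is the missing-at-random assumption, which would not correct relapse that earlier data do not predict and should be stated next to the results. The SAP is written in the past tense, so if results are already known the added analysis should be labelled as such.

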Specific Aim 1 (Phase II): Informed by Phase I findings, (approved in a previous IRB protocol #2016P000423), we aim to develop and determine the feasibility (by assessing the number of sessions attended and adherence to Relaxation Response practice) and acceptability (assessed using the Participant Feedback Survey) of an 8-session Relaxation Response Resiliency (SMART-3RP) program for parents of children with learning disabilities.

Hypothesis: The SMART-3RP virtual delivery will be feasible to implement and acceptable to parents of children with learning disabilities.

Primary Aim 2 (Phase III): To test the effectiveness of a pilot waitlist controlled trial on improving resiliency, as measured using the General Self-Efficacy Questionnaire, Current Experiences Scale, and the Visual Analogue 0-10 scales (including stress, distress, coping, and physical discomfort), and on improving stress reactivity (as measured by the Measure of Current Status-A), growth enhancement (as measured by the Cognitive and Affective Mindfulness Scale-Revised), and parental stress (as measured by the Parental Stress Scale). This will be assessed by comparing Baseline-3 mo. scores on primary and secondary outcome measures between the Immediate and Waitlist control groups.

Primary Hypothesis: Patients randomized to the Immediate group will report significantly greater scores on the primary outcomes (measures of resilience) and on the secondary outcomes (measures of stress reactivity, growth enhancement, and parental stress) at 3 mo. post enrollment.

Secondary Aims: Among participants randomized to both conditions, to investigate the extent of pre-post changes in primary and secondary outcomes (Immediate: assessments from baseline-3 mo.; Waitlist: from 3-6 mo.).

Secondary Hypothesis: Scores on primary and secondary outcome measures will improve from pre-post intervention.

Secondary Aim 2: Among immediate condition group only, to assess whether end-of-treatment (3 mo. post enrollment) improvements will be sustained at 6-mo. post enrollment.

Hypothesis: These end-of-treatment effects will show sustained improvement on primary and secondary outcome measures from 3 to 6-mo. Post enrollment.

Secondary Aim 3: To pilot test the end-of-treatment effects of the SMART-3RP on parents' stress levels using hair cortisol. A mixed effects models approach will be used to examine group

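### If the Parental Stress Scale is among the outcomes correlated with baseline parenting stress, that one correlation is expected to differ from zero even with no moderation

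*SAP*

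**What the plan says.** The last analysis in the SAP's Statistical Analyses section is an exploration: "we explored whether greater parenting stress at baseline was associated with greater changes in our proposed psychosocial outcomes among participants". The time window and statistic are given as "before treatment and end of treatment) using Pearson correlations". It is meant to support a later, larger trial, and its stated purpose includes "identification of a potential moderator of intervention effects".

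The SAP names neither the stress scale nor the outcomes in this analysis. The protocol does give an outcome list. Primary Aim 2 (section II) includes "parental stress (as measured by the Parental Stress Scale", and section VI, question 2(a), lists among the secondary outcomes "the Parental Stress Scale (PSS; to assess parental stress". It is the only instrument that the protocol assigns to parental stress. Nothing in the SAP removes it from the correlations.

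For the paired tests just before this analysis, "we evaluated the combined change from pre- to post-intervention across intervention group condition participants (using time 1 to time 2 data", with time 2 to time 3 used for wait-list parents. The SAP does not say whether that definition carries over to the correlations, or which stress score is the baseline for a wait-list parent.

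**The concern.** If the Parental Stress Scale is both predictor and outcome, the correlation sets X1 against X2 - X1. The first score stands on both sides, with opposite signs. A parent whose first score is high by chance will tend to fall back, so a negative correlation (positive if change is scored as improvement) is expected when every parent has the same treatment effect. Zero is then the wrong reference value for moderation.

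The analysis is labelled as a search for a moderator and is meant to inform a larger trial. A significant result on the scale closest to the hypothesis could be taken as a sign that more-stressed parents benefit more, when it shows only that scores fluctuate.

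**Working it through.** **Inputs.**
- Planned sample: "A total of approximately 70 participants will be recruited for this study" (protocol, section III, Recruitment).
- Allocation 1:1 and a time 2 response of 75% (SAP, Randomization and Statistical Analyses). 0.75 x 70 = 52.5, so 52 or 53 parents.
- Assumed, because the documents give no value: rho (correlation of pre and post scores) from 0.5 to 0.9; equal pre and post SDs; two-sided 5% test.

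The plan states no expected correlation, SD or power for this analysis, so there is no figure of its own to reproduce.

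**Expected correlation without moderation.** Let k = SD_post/SD_pre. Then

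corr(X1, X2 - X1) = (rho x k - 1) / sqrt(1 + k^2 - 2 x rho x k).

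At k = 1 this becomes -sqrt((1 - rho)/2). For rho = 0.7: -sqrt(0.30/2) = -0.387.

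**Chance of a significant result.** By the Fisher z approximation, this is Phi(atanh|r| x sqrt(n - 3) - 1.96). For rho = 0.7 and n = 52: atanh(0.387) = 0.408; 0.408 x 7 = 2.86; 2.86 - 1.96 = 0.90; Phi(0.90) = 0.82.

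**Mixed pairing.** Suppose baseline means time 1 for everyone while wait-list change runs from time 2 to time 3. With equal correlations between all visits, the wait-list covariance is rho - rho = 0. About half the sample is then uncoupled, and the pooled correlation is about half as large.

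| Assumed rho | Expected r, coupled | p<0.05, n = 52 | p<0.05, n = 70 | Simulated r, mixed pairing, n = 52 | p<0.05, mixed, n = 52 / n = 53 |
|---|---|---|---|---|---|
| 0.5 | -0.50 | 97% | 99% | -0.25 | 44% / 46% |
| 0.6 | -0.45 | 92% | 98% | -0.22 | 36% / 38% |
| 0.7 | -0.39 | 82% | 92% | -0.19 | 28% / 30% |
| 0.8 | -0.32 | 63% | 76% | -0.16 | 20% / 22% |
| 0.9 | -0.22 | 36% | 46% | -0.11 | 13% / 13% |

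The mixed-pairing columns are simulated (4,000 runs at n = 52; 20,000 at n = 53). Simulation of the coupled case, with the same treatment effect for every parent, agrees with the formula: at rho 0.7 and n = 52, mean r -0.38 and 83% significant.

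**Is it a treatment signal?** No. In the same simulation, untreated wait-list parents from time 1 to time 2 (26 of them, rho 0.7) also show a mean r of -0.38.

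**Sensitivity to the SDs.** The expected value reaches zero when k = 1/rho: 1.43 at rho 0.7, 1.11 at rho 0.9. At rho 0.7 and k = 1.1 it is still -0.28; at rho 0.9 and k = 1.1 it is only -0.02.

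**A test with the right null.** Regress the time 2 score on baseline score, arm and arm-by-baseline interaction. Under the no-moderation model the interaction test rejects in 4.7% to 5.6% of runs (n = 52 or 70, rho 0.5 to 0.9). Its precision is modest. With 26 per arm, rho 0.7 and unit SDs, the standard error of the slope difference is about sqrt(2 x (1 - 0.49)/26) = 0.20, so a 95% interval is about +/-0.39.

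**The case against.** The strongest reply is that the premise is inferred. The SAP of 2019 does not name the outcomes or the stress scale, and the list comes from a protocol of 2016. The sentence could mean that stress was related only to the other outcomes. That stands as a limit, and the point is therefore conditional. The protocol lists the scale and the SAP does not exclude it, so inclusion is the default reading, and one clause would settle it.

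A second reply is that little is touched. Counting the visual analogue ratings as four, the protocol's list holds about nine scores: self-efficacy, current experiences, four ratings, coping status, mindfulness and parental stress. Only the last contains baseline parenting stress in its change. This also stands, and the analysis is exploratory with no decision rule attached.

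A reader might go further and infer three things that the documents do not support:
- That a false moderator is all but certain. The rates fall to 36% at rho 0.9, and to between 46% and 13% under mixed pairing. No rho is given, and a growing post SD can remove the effect.
- That the correlation is wrong even as a description of who changes most. It is not: with rho below 1 and equal SDs, parents with higher first scores do have larger expected falls. What fails is crediting that to the programme.
- That the efficacy results are compromised. The between-group t-tests on change do not use this correlation.

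**Conclusion.** The point holds in a limited form. If the Parental Stress Scale is among the correlated outcomes, that one correlation has an expected value of -0.50 to -0.22 under no moderation (assumed rho 0.5 to 0.9, equal SDs). At 52 or 53 parents a test against zero would be significant in about 97% to 36% of trials when every parent's own pre-programme score is used, and in about 46% to 13% under mixed pairing. Both ranges are above the nominal 5%. The count of 52 or 53 applies the time 2 response target to the whole sample. Pooled change for wait-list parents also needs time 3, for which the SAP gives no retention figure.

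The result may be reported as regression to the mean, but not as a moderator. Severity is minor: one pair in one exploratory analysis, with the main comparison untouched.

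**What to change.** List the outcomes that enter the correlations, and say which stress score is the baseline for wait-list parents. Then either exclude parenting-stress change from the outcomes correlated with baseline parenting stress, or state that this pair is not interpreted as moderation.

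If moderation on this scale is of interest, use the randomised time 1 to time 2 data: regress the time 2 score on baseline score, arm and arm-by-baseline interaction, report the interval, and state that power is low.

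Oldham's method (change against the mean of pre and post) should not be the main remedy. It has no control contrast, and it is biased when true change varies between parents. If change has SD 0.5 and is independent of a baseline with SD 1, the raw correlation is 0 but Oldham's is 0.125/(0.5 x sqrt(1.0625)) = +0.24.

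Cost: a sentence or two in the SAP and, at most, one extra regression on data already collected. The price is one fewer exploratory correlation, or an interaction estimate with a wide interval.
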